## 2 OBJECTIVES AND ENDPOINTS

### 2.1 Primary

The primary objectives are:

- To evaluate the safety and tolerability of a single injection of VAX-24 at three dose levels administered to healthy adults 18 to 64 years of age.
- To compare the safety of VAX-24 to that of PCV20 administered to two control groups: 1) subjects 18 to 49 years of age; and 2) subjects 50 to 64 years of age.

Safety and tolerability will be assessed by measuring the incidence of solicited local and systemic adverse events (AEs), unsolicited AEs, serious adverse events (SAEs), new onset of chronic illness (NOCI), and medically attended adverse events (MAAEs):

- Percentage of subjects reporting solicited local reactions within 7 days after vaccination (redness, swelling, and pain at injection site) in each age group
- Percentage of subjects reporting solicited systemic events within 7 days after vaccination (fever, headache, fatigue, muscle pain, and joint pain) in each age group
- Percentage of subjects reporting unsolicited AEs within 1 month after vaccination in each age group
- Percentage of subjects reporting SAEs and NOCI within 6 months after the vaccination
- Percentage of subjects reporting AEs with a new onset or a worsening of a condition that prompts the subject to seek unplanned medical advice at a physician's office, urgent care center, or Emergency Department (MAAE).

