#### 6.1.3 Day 8 (+3 days)

The following procedures will take place at this visit:

- Visual inspection of injection site location
- Review of diary data with the subject; Investigator's assessment of severity and relationship to study vaccine
- Concomitant medications
- AE (solicited and unsolicited) and SAE evaluation

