#### **6.1.6 Months 3, 4, 5, 6 (90 to 180 days after Day 1 ( $\pm$ 5 days))**

These visits are follow-up phone calls for safety evaluation. The following procedures will take place at each visit:

- SAE, NOCI, and MAAE evaluation
- Concomitant medications or vaccines potentially related to SAE, NOCI, MAAE, or prohibited medications

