### 8.4 Electronic Patient Reported Outcome Data

This study will employ electronic transfers of external diary data generated from subjects recording solicited AEs and actions taken for 7 days post-vaccination within a validated system

that is 21 CFR Part 11 compliant. The Investigator is responsible for the adequacy and accuracy of data associated with severity and relationship to study vaccine.

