3.2. Safety Variables

Safety assessments performed during the study included solicited AE up to Day 8 and monitoring of unsolicited adverse events, physical examinations, measurement of vital signs, clinical laboratory evaluations including hematology, serum chemistry, and urinalysis.

The primary endpoints are:

- Percentage of subjects reporting solicited local reactions within 7 days after vaccination (redness, swelling, and pain at injection site) in each age group.
- Percentage of subjects reporting solicited systemic events within 7 days after vaccination (fever, headache, fatigue, muscle pain, and joint pain) in each age group.
- Percentage of subjects reporting unsolicited AEs within 1 month after vaccination in each age group.
- Percentage of subjects reporting SAEs, NOCIs, and MAAEs within 6 months after vaccination.

The secondary endpoint related to Safety assessments is:

- Percentage of participants with laboratory value abnormalities and/or potentially clinically significant laboratory values at 1 month after vaccination.

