6.5.1.2. Unsolicited Adverse Events

An unsolicited AE is an AE that is spontaneously reported by the subject or discovered by the Investigator. New onset of chronic illness(s) would be recorded as part of the collection of unsolicited AEs as specified in the visit procedures. Unsolicited AEs are collected separately from solicited AEs.

Solicited AEs continuing beyond 7 days will be flagged using rules given in Section 5.2 and described in separate summaries as explained in Section 6.5.1.3.

The definition of a treatment emergent AE (TEAE) is an event that occurs after vaccination and within the 28 days after vaccination (i.e., excluding those after a subject has given informed consent, but before vaccination):

- Onset (days) = Start date of AE – Date of Study Vaccine Administration + 1
- An AE is a TEAE if:
 - Onset \geq 1 and Onset \leq 28
 - For AEs with Onset=1 the time of onset of AE must be greater or equal to the time of vaccination to be considered a TEAE

Adverse events are summarized by subject, therefore, in any tabulation, a subject contributes only once to the count for a given adverse event (SOC or preferred term).

Unsolicited AEs will be coded using the Medical Dictionary for Regulatory Activities (MedDRA) and will be summarized by decreasing frequency of SOC and preferred term within SOC in the control group, as follows:

- [P] Any unsolicited TEAEs
- Possibly or probably related unsolicited TEAEs
- Unsolicited TEAEs leading to study withdrawal
- Any AE leading to death
- [P] Any SAE within 6 months after the vaccination by maximum relationship to study treatment. This summary will include serious solicited AEs.
- [P] Any NOCI within 6 months after the vaccination by maximum relationship to study treatment.
- [P] Any MAAEs within 6 months after the vaccination by maximum relationship to study treatment.

Following by-subject Listings will be provided:

- Pre-vaccination AEs (non-emergent)

- All unsolicited TEAEs
- All Serious post-vaccination AEs, NOCIs and MAAEs

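### SAP 6.5.1.2 lists the primary MAAE summary under unsolicited AEs and brings solicited events back only for SAEs, so as written it leaves out non-serious solicited reactions that led to a medical visit

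*SAP*

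**What the plan says.** **Endpoint.** Protocol 2.1 gives the MAAE endpoint as "Percentage of subjects reporting AEs with a new onset or a worsening of a condition that prompts the subject to seek unplanned medical advice", followed by the places of care. SAP 3.2 has "Percentage of subjects reporting SAEs, NOCIs, and MAAEs within 6 months after vaccination". Neither limits the endpoint to unsolicited events. Under protocol 7.1.2 a solicited AE is itself a kind of AE.

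**Tabulation.** SAP 6.5.1.2 opens its list of summaries with "Unsolicited AEs will be coded using the Medical Dictionary for Regulatory Activities (MedDRA) and will be summarized by decreasing frequency of SOC". The MAAE item, tagged as primary, reads "P] Any MAAEs within 6 months after the vaccination by maximum relationship to study treatment". The SAE item in the same list carries an extra sentence: "This summary will include serious solicited AEs". The MAAE item has no such sentence.

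**Collection.** The design text (protocol 3.1, SAP 2.1) has MAAEs collected up to 6 months after vaccination. The Day 8 visit lists "AE (solicited and unsolicited) and SAE evaluation"; Days 15 and 29 list unsolicited AE and SAE evaluation. The Month 3 to 6 calls are the first to list "SAE, NOCI, and MAAE evaluation". Protocol 8.4 describes subjects "recording solicited AEs and actions taken for 7 days post-vaccination within a validated system", and protocol 5.11 has staff review the action taken at the clinic visit.

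**The concern.** The table that reports a primary safety endpoint looks narrower than the endpoint. The authors saw that a list of unsolicited AEs would omit solicited events and corrected this for SAEs, but they did not do so for MAAEs. A programmer following the text would leave solicited events out.

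The omission would be selective. Solicited reactions in the first week are the events most plausibly caused by the vaccine: protocol 5.11 records local ones automatically as probably related, and SAP 6.5.1.1 treats all of them that way. The MAAE table is split by relationship, so the missing events would come from its related rows. Those rows bear most directly on the comparison of dose levels with PCV20 in the primary objective. Attended reactions might also rise with reactogenicity, in which case the shortfall would differ between arms. SAP section 7 declares no change from the protocol analyses, so a reader of the study report would not know that the table was narrower.

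**Working it through.** The plan gives no MAAE rate, precision or power, so there is no figure on this point to reproduce. The check is a reading of the sections against each other, followed by an illustration under assumed rates.

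**Step 1: follow one hypothetical subject.** Injection-site swelling starts on Day 2, the subject visits urgent care on Day 3, the swelling resolves by Day 6, and the event is not serious.

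| Question | Source | Answer |
|---|---|---|
| Does it meet the endpoint? | Protocol 2.1; SAP 3.2 | Yes: an AE that prompted unplanned medical advice |
| Where is it recorded? | Protocol 5.11 | In the electronic diary |
| Does it enter the unsolicited stream? | Protocol 5.12, 7.5.1 | No: diary terms do so only outside or beyond the solicited period |
| Is it in the SAE summary? | SAP 6.5.1.2 | No: not serious |
| Is it in the solicited AE summaries? | SAP 6.5.1.1 | Yes, by severity, day, onset and duration, but not as medically attended |
| Is it in the combined summaries? | SAP 6.5.1.3 | No: these take solicited AEs continuing past 7 days, and none is an MAAE summary |
| Is it in the MAAE summary? | SAP 6.5.1.2 | Not under the lead-in; only if the word *any* in the item overrides it |

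**Step 2: the same reaction, but continuing past Day 7.** SAP 5.2 puts it on the unsolicited AE page, where it could be identified as an MAAE. SAP 6.5.1.2 then says continuing solicited AEs are described in separate summaries. Whether they also count in the MAAE table is not stated.

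**Step 3: capture.** MAAE evaluation is first named at Month 3. But AEs are evaluated on Days 1, 8, 15 and 29, the action taken is among the AE data fields in protocol 7.5.2, and the diary review covers it. What is absent is a named MAAE question at the early visits. Footnote c of the schedule, on collection after Day 29, omits MAAEs in the protocol and names them in the SAP.

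**Step 4: illustration only.** Let q be the share of subjects with a non-serious attended solicited reaction and no other MAAE. The documents do not give q, so a range is assumed. With 200 subjects per Phase 2 arm (protocol Table 4):

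- expected number missed per arm = 200q
- probability of missing at least one = 1 − (1 − q)^200

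This at-least-one formula also reproduces the plan's Phase 1 detection figures: 1 − 0.85^16 = 0.926 (stated as at least 92%) and 1 − 0.90^16 = 0.815 (stated as 81%).

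| Assumed q | Missed per arm of 200 | Missed among 600 VAX-24 subjects | Chance of missing at least one in an arm |
|---|---|---|---|
| 0.5% | 1 | 3 | 63% |
| 1% | 2 | 6 | 87% |
| 2% | 4 | 12 | 98% |
| 3% | 6 | 18 | 99.8% |

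If a further 10% of an arm (20 subjects, also assumed) had some other MAAE, the arm's count would be short by 2/22 = 9% at q = 1% and by 6/26 = 23% at q = 3%.

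**The case against.** The best defence is textual. No sentence excludes solicited events, and the item says *any* MAAEs. Other items in the list carry the word unsolicited, while those for deaths, SAEs, NOCIs and MAAEs do not. This stands to the extent that the exclusion is implied and not declared. It does not settle the matter: the lead-in governs the whole list, and the SAE item, which also says *any*, still needed its own sentence to bring solicited events in.

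A second defence is that the reactogenicity signal is not lost. Solicited reactions are primary endpoints in their own right, tabulated by event, severity and day, and serious ones are in the SAE table. That is correct. What would be lost is the information that a non-serious reaction led to medical care, which is what the MAAE endpoint exists to report. Nor does any decision rule depend on the table, since the SAP plans formal testing only for immunogenicity. With attended-reaction rates assumed at 3% and 1%, 6/200 against 2/200 gives a Fisher p-value of 0.28.

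A reader might infer three stronger things that the documents do not support:

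- **That the endpoint itself excludes solicited reactions.** It does not; the gap lies in the SAP tabulation.
- **That MAAEs before Month 3 go uncollected.** The design text sets collection up to 6 months with no Month 3 start, AEs are evaluated at every early visit, and the action taken is recorded. The later calls name MAAEs because follow-up is by then limited to SAEs, NOCIs and MAAEs. Whether the forms carry an MAAE flag cannot be known, because the completion guidelines and output shells are not among the documents.
- **That reactions continuing past Day 7 are dropped.** The SAP leaves this open.

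**Conclusion.** The point holds as a mismatch between a primary endpoint and the summary meant to report it. Followed as written, SAP 6.5.1.2 does not count non-serious solicited reactions on Days 1 to 7 that led to a medical visit, and no other planned summary recovers them as MAAEs. For solicited reactions continuing past Day 7 the SAP is silent. This rests on reading the lead-in as governing the list. If the sponsor intends the broader reading, the SAP should say so; if it intends the narrower one, section 7 should declare it.

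The size cannot be computed. The figures of 1 to 6 subjects per arm, and 9% to 23% of an arm's count, follow from assumed rates and from assuming that affected subjects have no other MAAE. They show that a handful of subjects could matter to a table with small counts; they do not estimate the loss. Sample size and alpha are unaffected.

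**What to change.** Add to the MAAE item in SAP 6.5.1.2: *This summary will include medically attended solicited AEs, including those continuing beyond 7 days.* State that these are identified from the diary action-taken data as reviewed by the Investigator at Day 8. This assumes that the action-taken item can show an unplanned medical visit; if it cannot, a yes/no item is needed at the Day 8 review. The programming specification should also cover MedDRA coding of the added diary events and the relationship category they take, since the table is laid out by both.

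For consistency, name MAAE evaluation at Days 8, 15 and 29 (protocol 6.1.3 to 6.1.5), and align footnote c of the protocol's Appendix A with the SAP version, which names MAAEs. The SAP change should be made before the interim database lock for the Day 29 Analysis, because primary safety outputs are produced then and their scope is settled beforehand.

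The cost is one SAP sentence, short edits to the visit lists and a little more programming. The MAAE percentage may come out slightly higher in all arms.

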6.5.1.3. Combined Solicited and Unsolicited Adverse Events

Solicited AEs continuing beyond 7 days will be recorded by the sites and flagged using rules given in Section 5.2. They will be coded by MedDRA and following summary by decreasing frequency of SOC and preferred term within SOC will be provided:

- Solicited TEAEs continuing beyond 7 days
- Combined solicited TEAEs continuing beyond 7 days and unsolicited TEAEs

Following by-subject Listings will be provided:

- All solicited TEAEs continuing beyond 7 days

6.5.2. Laboratory Data

- A summary describing pregnancy tests results, as well as results for Human Immunodeficiency Virus (HIV), Hepatitis B surface antigen (HBsAg) and Hepatitis C Virus (HCV) tests at Baseline will be presented. The list of Baseline test results to be described is given in *Table 2*. Reflex testing (HBsAg confirmation, HCV RNA qual, HIV1AB, HIV2AB) will be described only for subjects with initial positive test.

Table 2 Baseline Laboratory Tests

Panel	Sample	Parameter	Screening	Day 1
Immunochemistry	Serum	Pregnancy (serum)	X	
Immunochemistry	Serum	HBsAg	X	
Immunochemistry	Serum	HBsAg confirmation	X	
Immunochemistry	Serum	HCV Ab	X	
Immunochemistry	Serum	HCV RNA qual	X	
Immunochemistry	Serum	HIV 1/2 Ab-p24 Ag	X	
Immunochemistry	Serum	HIV1AB	X	
Immunochemistry	Serum	HIV2AB	X	
Urinalysis	Urine	Pregnancy (urine)		X

- The actual value and change from Baseline to Day 29 and to Early Study Discontinuation will be summarized for each clinical laboratory parameter, including hematology, clinical chemistry, and urinalysis. The complete lists of parameters can be found in *Table 3*.
- [S] A shift table from Baseline to Day 29 and to Early Study Discontinuation presenting abnormal values for each parameter will also be presented. Clinical laboratory values will be expressed using conventional international system of units (SI). In the event of repeat values, the last non-missing value per study day/time will be used. Clinically significant out-of-range lab results will be reported as adverse events by Investigators. Clinical significance will therefore not be reported in the laboratory outputs.

Table 3 Laboratory Parameters Collected during the Study

Panel	Sample	Parameter	Screening	Day 29 (or Early Study Discontinuation)
Hematology	Blood	Hemoglobin	X	X
Hematology	Blood	White blood cell count (absolute)	X	X
Hematology	Blood	Neutrophils (absolute)	X	X
Hematology	Blood	Eosinophils (absolute)	X	X
Hematology	Blood	Platelet count	X	X
Chemistry	Serum	Albumin	X	X
Chemistry	Serum	Alkaline phosphatase	X	X
Chemistry	Serum	Alanine aminotransferase (ALT)	X	X
Chemistry	Serum	Aspartate aminotransferase (AST)	X	X
Chemistry	Serum	Bilirubin (Total)	X	X
Chemistry	Serum	Bilirubin (Direct)	X	X
Chemistry	Serum	Blood urea nitrogen	X	X
Chemistry	Serum	Calcium	X	X
Chemistry	Serum	Carbon dioxide	X	X
Chemistry	Serum	Chloride	X	X
Chemistry	Serum	Cholesterol and triglycerides	X	X
Chemistry	Serum	Creatinine	X	X
Chemistry	Serum	Glucose (random)	X	X
Chemistry	Serum	Gamma-glutamyl transferase (GGT)	X	X
Chemistry	Serum	Lactate dehydrogenase	X	X
Chemistry	Serum	Phosphate	X	X
Chemistry	Serum	Potassium	X	X
Chemistry	Serum	Sodium	X	X
Chemistry	Serum	Total serum protein	X	X
Chemistry	Serum	Uric acid	X	X
Urinalysis	Urine	Specific Gravity (SG)	X	X
Urinalysis	Urine	pH	X	X
Urinalysis	Urine	Glucose	X	X
Urinalysis	Urine	Protein (Total)	X	X
Urinalysis	Urine	Ketones	X	X
Urinalysis	Urine	Bilirubin	X	X
Urinalysis	Urine	Urobilinogen	X	X
Urinalysis	Urine	Hemoglobin	X	X
Urinalysis	Urine	Leucocyte Esterase	X	X
Urinalysis	Urine	Nitrite	X	X

All laboratory data will be provided in data listings.

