## 5.6.2 Safety Laboratory Assessments

Biological samples will be collected for the following clinical laboratory tests and shipped to the central laboratory for analysis:

**Hematology:** Hemoglobin, White blood cell count (absolute), Neutrophils (absolute), Eosinophils (absolute), Platelet count

**Clinical Chemistry:** Albumin, Alkaline phosphatase, Alanine aminotransferase (ALT), aspartate aminotransferase (AST), Bilirubin (total and direct), Blood urea nitrogen, Calcium, Carbon dioxide, Chloride, Cholesterol and triglycerides, Creatinine, Glucose (random), Gamma-glutamyl transferase (GGT), Lactate dehydrogenase, Phosphate, Potassium, Sodium, Total serum protein, Uric acid

**Urinalysis:** Specific gravity, pH, Glucose, Protein (Total), Ketones, Bilirubin, Urobilinogen, Hemoglobin, Leucocyte esterase, Nitrite

**Serology:** HIV 1/2 antibody/antigen test, HBsAg, Hepatitis C virus antibody (HCV Ab)

**Pregnancy:** Serum test at Screening visit only

Urine pregnancy tests will be conducted at the site using a dipstick before vaccination.

Screening safety lab results are required for subject eligibility in order to be enrolled in the study at Day 1. Screening safety labs will be used as baseline if a subject meets eligibility for enrollment into the study. Screening laboratory tests reported as minor abnormalities are considered acceptable if not clinically significant (eg, MCV). Repeating the screening tests once is permitted for out-of-range values, provided there is an alternative explanation for the out-of-range value. This alternative explanation should be documented in the subject's source documents.

Unscheduled laboratory tests will be performed if indicated by a change in medical condition (including clinically significant abnormal values). The volume to be collected will be appropriate to the tests performed. The toxicity grading scales for clinical laboratory values ([FDA 2007](#)) must be used when assigning severity to an out-of-range laboratory value; however, not all out of range laboratory values are considered AEs and need to be evaluated according to [Section 7.1.1, Adverse Events](#).

Further details regarding specimen collection, processing, and shipping will be provided in the Central Laboratory Manual.

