## 7 SAFETY

### 7.1 Definitions

#### 7.1.1 Adverse Event

An adverse event is any untoward medical occurrence in a study subject, regardless of the suspected causal relationship with study vaccine.

The definition of an AE includes:

- A new-onset symptom or disease
- An exacerbation of a pre-existing symptom or disease
- A new-onset laboratory abnormality considered by the Investigator to be clinically significant
- A new-onset symptom or disease that occurs as a result of a protocol-specified procedure

The definition of an AE does **not** include:

- A pre-existing symptom or disease that does not worsen during the study (even if first disclosed by the subject after the start of the study)
- A medical or surgical intervention such as surgery, endoscopy, tooth extraction, or transfusion (although the condition leading to the procedure or a complication from the procedure may be an AE)
- An uncomplicated pregnancy
- A dosing error without any resulting signs or symptoms
- Any other situation where an untoward medical occurrence has not occurred (eg, hospitalization for cosmetic elective surgery or social admissions)

The definition of a treatment emergent AE (TEAE) is an event that occurs after vaccination and within the 28 days after vaccination (ie, excluding those after a subject has given informed consent, but before vaccination).

The definition of a NOCI includes:

A new-onset of chronic illness is a disease or condition, that is newly diagnosed, requires ongoing medical attention and/or limits activity of daily living, eg, heart disease, cancer, diabetes.

The Investigator will attempt to establish a diagnosis based on signs, symptoms, and other clinical information. Whenever possible, the Investigator will report an AE as a diagnosis rather than one or more signs or symptoms. If a clinically significant laboratory abnormality meets the

definition of an AE, a diagnosis or clinical signs and symptoms rather than the abnormal laboratory finding should be reported if possible. If no diagnosis is known and clinical signs and symptoms are not present, but the laboratory abnormality is clinically significant by itself, then it should be reported as the AE.

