## **8.5 Laboratory Data**

This study will employ electronic transfers of external laboratory data generated from clinical specimens collected by the Investigator. The Investigator is responsible for the adequacy and accuracy of data associated with collection of these specimens, and for determining clinical significance for all out of range values.

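### The potentially clinically significant part of the secondary laboratory endpoint has no by-arm percentage, and adverse event reporting cannot reliably or completely supply it

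*SAP*

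**What the plan says.** SAP 3.2 states the secondary safety endpoint as: "Percentage of participants with laboratory value abnormalities and/or potentially clinically significant laboratory values at 1 month after vaccination". Protocol 2.2 has the same endpoint and pairs it with an objective that compares three VAX-24 dose levels with PCV20 in subjects aged 50 to 64.

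SAP 6.5.2 plans summaries of actual value and change from baseline for each parameter, and one laboratory output marked [S] for the secondary endpoint: "A shift table from Baseline to Day 29 and to Early Study Discontinuation presenting abnormal values for each parameter will also be presented". It goes on: "Clinically significant out-of-range lab results will be reported as adverse events by Investigators", and then: "Clinical significance will therefore not be reported in the laboratory outputs". The section ends: "All laboratory data will be provided in data listings".

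The protocol treats the size and meaning of an abnormal value as important. Section 5.6.2 says the FDA 2007 toxicity grading scales "must be used when assigning severity to an out-of-range laboratory value". Section 8.5 makes the investigator responsible for "determining clinical significance for all out of range values". On recording, section 7.1.1 says that when a significant laboratory abnormality meets the AE definition, "a diagnosis or clinical signs and symptoms rather than the abnormal laboratory finding should be reported if possible".

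**The concern.** One part of a declared secondary endpoint is a percentage of participants with PCS values, yet a rule in the SAP keeps significance out of the laboratory tables. A reader of the study report who wants the share of each arm with such a value at Day 29 would not find it. The AE tables offered in its place are built on different terms and a different time window.

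At stake is a between-arm safety comparison in a first-in-human, dose-finding trial. The planned tables would show how often each parameter moved outside its normal range, and how its average moved. They would not show how many participants in each dose group had a marked value.

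**Working it through.** **1. Match the endpoint to the outputs.**

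- Laboratory abnormalities: [S] shift table, per parameter. Output present.
- PCS values, read as investigator-judged significance: excluded from the laboratory outputs by SAP 6.5.2. No by-arm percentage.
- PCS values, read as crossing a threshold: no thresholds and no table by toxicity grade in either document. No by-arm percentage.

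Protocol 9.6 does not fill the gap. It describes no laboratory analysis, and 9.6.5 covers concomitant medications only.

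**2. Can the AE tables supply the count? The terms.** SAP 6.5.1.2 tabulates unsolicited AEs by system organ class and preferred term. Under protocol 7.1.1 a significant value is recorded as a diagnosis or symptoms where possible, so a preferred term need not identify a laboratory value. If there is no diagnosis and no symptom, the same section says that the abnormality itself is the AE. Some PCS values would therefore carry a laboratory term and others would not.

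**3. The new-onset condition.** The laboratory item in the AE definition covers new-onset abnormalities. Inclusion criterion 5 admits minor abnormalities at baseline. A value that worsens from an abnormal baseline does not clearly qualify under that item.

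**4. The dates.** Inputs: onset day = AE start date − vaccination date + 1, and treatment-emergent if onset is 1 to 28 (SAP 6.5.1.2); laboratory sample 28 days after vaccination (SAP 2.1); visit window ±3 days (protocol 6.1.5).

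- Nominal sample: 28 + 1 = 29, which reproduces the plan's Day 29.
- Permitted visit days: 29 − 3 = 26 to 29 + 3 = 32, so 7 days.
- Assume that the AE start date is the sample date. Days 26 to 28 count (3 of 7). Days 29 to 32 do not (4 of 7).
- The accompanying text says within 28 days after vaccination, which under the SAP's own formula reaches onset day 29. On that reading 4 of 7 days count and 3 of 7 do not. All 7 would need a limit of 32.

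A finding dated to Days 29 to 32 that is not serious, not a new-onset chronic illness (NOCI) and not medically attended (MAAE) enters none of the treatment-emergent, SAE, NOCI or MAAE tables. The AE listings in SAP 6.5.1.2 cover the same categories plus pre-vaccination events, so it is missing there too.

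**5. Illustration of size.** The documents give neither a PCS rate nor the spread of visit days, so both are assumed. Take a true rate of 5%, which is 10 of 200 per arm, with every case reported under a laboratory term and dated to its sample. Let s be the share of visits on Days 29 to 32. The treatment-emergent table then shows 5% × (1 − s):

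- s = 25%: 7.5 of 200, 3.75%
- s = 4/7 (57%): 4.3 of 200, 2.1%
- s = 75%: 2.5 of 200, 1.25%
- s = 90%: 1 of 200, 0.5%

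The effects in steps 2 and 3 would come on top of this and do not depend on the date assumption.

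**The case against.** The strongest reply is that the endpoint joins its two parts with and/or, and the first part has its [S] table. The SAP also plans value and change summaries by treatment group, with minimum and maximum (SAP 6.2.1, 6.5), and lists all laboratory data. An asymptomatic, isolated finding at Day 29 would be reported as an AE under its own name. The date argument rests on an assumption about AE start dates that neither document states.

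All of this is correct, and it limits the point to the PCS part. It does not supply that part. Value and change summaries do not count participants with marked values, a listing is not a percentage by arm, and SAP 2.7 keeps individual listings out of the Day 29 delivery. The diagnosis-first rule and the new-onset condition apply whatever date is used.

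A reader might infer four stronger things that the documents do not support:

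- *That the planned tables could not show a dose-related laboratory signal, because chance abnormalities across many tests would swamp it.* The shift table is per parameter and runs from baseline, with a concurrent PCV20 arm, so a count of any abnormality across all tests describes no planned output.
- *That PCS values would appear nowhere.* Some would appear in the AE tables, and all values are listed.
- *That every out-of-range value must be graded and every significance judgement is a database field.* Protocol 5.6.2 fixes the scale for use when severity is assigned, and 8.5 assigns a responsibility. Neither says what is captured.
- *That the statement of no changes in SAP section 7 is wrong.* The protocol defines no laboratory analysis for the SAP to depart from.

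**Conclusion.** The point holds for the PCS part of the endpoint and not for the endpoint as a whole. PCS is undefined in both documents, and no planned output gives its percentage by arm. Under the SAP 6.5.2 sentence, AE reporting is the only substitute, and it is unreliable and incomplete.

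That there is no definition and no by-arm percentage rests on the text alone. The loss through the treatment-emergent window (4 of 7 visit days under the onset rule as written, 3 of 7 under the wider reading) assumes that the AE start date is the sample date. The illustration in step 5 also assumes the PCS rate and the spread of visits, so it shows a range and not an estimate. The change should be made because a stated rule leaves part of a declared safety endpoint unreported by arm, and the laboratory values needed to report it are already collected.

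**What to change.** In SAP 6.5.2:

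- Delete the sentence that excludes clinical significance from the laboratory outputs.
- Define PCS for the analysis by the FDA 2007 toxicity scale named in protocol 5.6.2, for example Grade 2 or higher, together with any worsening in grade from baseline. Derive the grades by program from the collected values, for the parameters on that scale. Settle the definition before the interim database lock.
- Add an [S] table of n/N (%) of subjects at Day 29 by grade, by treatment group and age group.
- Add investigator-judged significance if it is captured in the database.
- Keep the shift table.

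Separately, reconcile the onset limit of 28 with the text that says within 28 days after vaccination. Widening that limit would not by itself produce a PCS percentage.

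The cost is SAP wording, one extra table shell and the grade programming, with no new samples or visits. The drawback is that parameters not on the scale stay in the shift table only. The scale is not reproduced in these documents, so its coverage of SAP Table 3 must be checked and stated.
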